4.2. Survey plan

The patients should have colitis ulcerative in the active moderate or severe phase (only when an existing treatment does not work) and newly receive Humira.

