Code, name of disease: Obtain the MedDRA/J PT code and PT from the indication of Humira described in the survey form. If the indication is 'other', obtain the indication from "[Humira UC] indication, other detailed coding".

(10) Severity prior to administration

Four stages of "physician's global assessment" at first administration in "Effectiveness assessment (partial Mayo-score)" of the survey form: remission phase, mild, moderate and severe

Select the data dated before the first administration date. If the date is behind the first administration date, select "no assessment". If the date is not provided or unknown, select

"unknown".

(11) Complications

Presence/absence: Refer to the "presence/absence of complications" defined in "10.1 General".

Number of described complications: the number of PT codes encoded by MedDRA/J. If more than 1 identical PT code is found in a patient, count the PT as 1. Describe "0" for the case with no complications.

Term: Describe the PT of complication encoded by MedDRA/J. Arrange detailed classification of complication, the name of complication disease name, a serial number of the complication per patient. Leave the column blank for the case with no descriptions.

(12) Route of administration

Describe it as "SC".

(13) Maximal dose (a day/volume)

The daily maximum dose Select the largest number in "administration status (dose and administration) defined in "10.1 General" per patient.

(14) The mean dose (a day/volume)

The mean daily dose

It should be the value of "total dose/total dosing times" based on the "administration status (total dosing time, total dose)" defined in "10.1 General".

(15) Unit

Use "MG".

(16) daily dosing frequency (the maximum)

Use "1".

(17) Period for administration

The value of "total dosing time" based on "administration status (total dosing time, total dose)" defined in "10.1 General".

(18) Concomitant medications

Drug code, the principal drug name: arrange them with sequence with the priority of concomitant medications for colitis ulcerative per patient, and choose the top concomitant medication. If there is no concomitant medication, leave the drug code column blank, and the name of the primary drug "null".

Number of descriptions: count the number of drug codes arranged as mentioned above. If more than 1 identical drug code is found in a patient, count it as 1. Describe "0" for the case with no concomitant medications.

(19) Effectiveness level

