13.3. Effectiveness

"3.1.1 Changes in Mayo score (Observed Case)"

Patients for analysis: patients in the effectiveness analysis group

Analysis objective: to show Mayo score and the changes in Mayo score per assessment period.

Analysis item: calculate the number of patients in the analysis groups.

Calculate the number of target patients, the mean and standard deviation of Mayo score, the mean and standard deviation of changes in Mayo score for each assessment period, and conduct a paired-t test which compares the values at the initial administration.

Note: Follow "12.3 Assessment period for Mayo score" for Time Allowance of assessment period.

The analysis covers only the patients with the assessment applicable to Time Allowance of the first administration and each assessment period.

Multiplicity in the test will be adjusted by the Bonferroni method.

"3.1.2 Changes in the remission rate at each point of Mayo score (Observed Case)"

Patients for analysis: patients in the effectiveness analysis group

Analysis objective: to show the remission rate of Mayo score per assessment period.

Analysis item: calculate the number of patients in the analysis groups.

Calculate the number of target patients, the percentage to the number of patients who achieved a remission and the number of target patients, 95%CI of the remission rate, and conduct a McNemar test for the first administration per assessment period.

In addition, prepare a line plot to describe the percentage to the target patients among the patients who achieved a remission per assessment period.

X-axis: assessment period (in week)

Y-axis: percentage (%)

Note: Follow "12.3 Assessment period for Mayo score" for Time Allowance of assessment period.

The analysis covers only the patients with the assessment applicable to Time Allowance of the first administration and each assessment period.

For the confidence interval, use the Clopper-Pearson's confidence interval.

Refer to "10.3 Effectiveness analysis" for the calculation method and remission rate.

"3.1.4 Changes in partial Mayo score (Observed Case)"

Patients for analysis: patients in the effectiveness analysis group

Analysis objective: to show partial Mayo score and the changes in partial Mayo score per assessment period.

Analysis item: calculate the number of patients in the analysis groups.

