Calculate the number of target patients, the mean and standard deviation of partial Mayo score, the mean and standard deviation of changes in partial Mayo score for each assessment period, and conduct a paired-t test which compares the values at the initial administration.

In addition, calculate the mean of the mean days to the final assessment and the standard deviation.

Note: Follow "12.4 Assessment period for partial Mayo score" for Time Allowance of assessment period.

The analysis covers only the patients with the assessment applicable to Time Allowance of the first administration and each assessment period.

Multiplicity in the test will be adjusted by the Bonferroni method.

"3.1.5.1 Changes in the remission rate at each point of partial Mayo Score (Observed Case)"

Patients for analysis: patients in the effectiveness analysis group

Analysis objective: to show the remission rate of partial Mayo score per assessment period.

Analysis item: calculate the number of patients in the analysis groups.

Calculate the number of target patients, the percentage to the number of patients who achieved a remission and the number of target patients, 95%CI of the remission rate, and conduct a McNemar test for the first administration per assessment period.

In addition, prepare a line plot to describe the percentage to the target patients among the patients who achieved a remission per assessment period.

X-axis: assessment period (in week)

Y-axis: remission rate (%)

Note: Follow "12.4 Assessment period for partial Mayo score" for Time Allowance of assessment period.

The analysis covers only the patients with the assessment applicable to Time Allowance of the first administration and each assessment period.

For the confidence interval, use the Clopper-Pearson's confidence interval.

Refer to "10.3 Effectiveness analysis" for the calculation method and remission rate.

"3.1.5.2 Changes in the remission rate (NRI) at each point of partial Mayo Score"

Patients for analysis: patients in the effectiveness analysis group

Analysis objective: to show the remission rate of partial Mayo score per assessment period.

Analysis item: calculate the number of patients in the analysis groups.

Calculate the number of target patients, the percentage to the number of patients who achieved a remission and the number of target patients, 95%CI of the remission rate, and conduct a McNemar test for the first administration per assessment period.

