In addition, prepare a line plot to describe the percentage to the target patients among the patients who achieved a remission per assessment period.

X-axis: assessment period (in week)

Y-axis: remission rate (%)

Note: Follow "12.4 Assessment period for partial Mayo score" for Time Allowance of assessment period.

The analysis covers only the patients with the assessment applicable to Time Allowance of the first administration and each assessment period.

For the confidence interval, use the Clopper-Pearson's confidence interval.

Refer to "10.3 Effectiveness analysis" for the calculation method and remission rate.

NRI: when it is unknown whether the remission is achieved, impute the data without remission.

"3.1.7.1 Remission rate at Week 52 in patients who achieved a remission at Week 8 of administration based on partial Mayo score"

Patients for analysis: Patients in the effectiveness analysis group (the patients who did not achieve a remission when the administration was started but achieved the remission at Week 8 of administration in partial Mayo score)

Analysis objective: to show the remission rate of partial Mayo score at Week 52 of administration in patients in the analysis group.

Analysis items: calculate the number of target patients, the percentage to the number of patients who achieved a remission at Week 52 of administration and the target patients, and the confidence interval of the remission rate. (calculate them in both Observed Case and NRI patterns)

Note: the patients for analysis should have partial Mayo score at the first administration and Week 8 of administration and achieved a remission at Week 8 of administration except those who had already achieved a remission in partial Mayo score at the first administration.

Follow "12.4 Assessment period for partial Mayo score" for Time Allowance of assessment period.

For the confidence interval, use the Clopper-Pearson's confidence interval.

"3.1.7.2 Remission rate at Week 52 in patients who achieved the response as an index of partial Mayo score at Week 8 of administration"

Patients for analysis: Patients in the effectiveness analysis group (the patients who achieved a response at Week 8 of administration in partial Mayo score)

Analysis objective: to show the remission rate of partial Mayo score at Week 52 of administration in patients in the analysis group.

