Analysis items: calculate the number of all patients, the percentage to the number of patients who achieved a remission in partial Mayo score and all patients, the number of patients who failed to achieve a remission in partial Mayo score and the percentage to number of all patients, the tests for remission (Fisher's exact test for nominal-scale factors and Man-Whitney's u test for ordinal-scale factors) per the following patient background factor:

Note: Refer to "3.4 Aggregation for effectiveness per patient background factor (general improvement rate)" for patient background factors.

"3.5 Changes in CPR level"

Patients for analysis: patients in the effectiveness analysis group

Analysis objective: to show measured CPR levels at each assessment period.

Analysis items: calculate CRP's summary statistics (number of cases, mean, standard deviation, minimum value, 1st quartile value, the median, 3rd quartile value and the maximum value) per assessment period.

Note: Follow "12.6 Assessment period for CRP" for Time Allowance of assessment period.

The analysis covers only the patients with the assessment applicable to Time Allowance of the first administration and each assessment period.

"3.6 The status of corticosteroid use and the remission in partial Mayo score in patients who used corticosteroids when administration was started (Observed Case)"

Patients for analysis: patients in the effectiveness analysis group

Analysis objective: to show the status of corticosteroid use and with/without remission in partial Mayo score per assessment period in patients who concomitantly used corticosteroids when administration was started

Analysis items: calculate the number of target patients, the percentage to the number of patients with/without concomitant use of corticosteroids and to the number of target patients, and the percentage to the number of patients who achieved/failed to achieve a remission in partial Mayo score and to the number of target patients.

Note: The target patients to be counted in each assessment period shall receive Humira in each Time Allowance defined in "12.4 Assessment period of partial Mayo score".

The target patients who concomitantly used corticosteroids at each assessment period shall receive corticosteroids at each scheduled date defined in "12.4 Assessment period of partial Mayo score".

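### Four remission tables do not separate patients already in remission at first administration; this matters most in Table 3.4.1, and the other three need one added line

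*SAP*

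**What the plan says.** The survey is aimed at active disease: "The patients should have colitis ulcerative in the active moderate or severe phase" (SAP 4.2; Protocol section 3 agrees). SAP section 8 lists two reasons for exclusion from the effectiveness analysis group: not the surveyed disease, and effectiveness not assessable. Neither is stated to cover remission at the start. The remission definitions in SAP 10.3 carry no baseline condition.

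In SAP 13.3, Tables 3.1.2 (full Mayo), 3.1.5.1 (partial Mayo, observed case) and 3.1.5.2 (partial Mayo, NRI) use that group with one filter: "The analysis covers only the patients with the assessment applicable to Time Allowance of the first administration and each assessment period". The NRI table adds only that "when it is unknown whether the remission is achieved, impute the data without remission". All three give a rate, a Clopper-Pearson interval and a line plot, and "conduct a McNemar test for the first administration per assessment period".

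Table 3.4.1 takes partial Mayo remission at final assessment as a primary endpoint and instructs the analyst to "calculate the number of all patients, the percentage to the number of patients who achieved a remission in partial Mayo score and all patients". It states no further filter and no paired test. Partial Mayo score is one of the background factors tested.

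Table 3.1.7.1, from the same group, is limited to "the patients who did not achieve a remission when the administration was started" and who were in remission at Week 8. Its note repeats the restriction: "except those who had already achieved a remission in partial Mayo score at the first administration".

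**The concern.** A patient in remission before the first dose can keep remission but cannot gain it. Where such patients stay in numerator and denominator, the displayed rate combines two quantities, and the reader cannot separate them. The exclusion in Table 3.1.7.1 would be redundant if the effectiveness analysis group could not contain these patients, so the SAP allows for them.

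More is at stake in Table 3.4.1. Finding factors that affect effectiveness is a stated aim (Protocol section 1, SAP 4.1). If a low baseline score partly is the outcome, its association with remission says little about the drug. For any other factor, levels that differ in their share of baseline remitters would differ in remission rate for that reason alone.

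**Working it through.** **Plan's own figure.** Protocol Table 1: 1500 × (1 − 0.70) × (1 − 0.30) = 315 patients assessed. With p = 0.30, the half-width is 1.96 × √(0.30 × 0.70 / 315) = 0.0506, giving 24.9 to 35.1, or ±5.1. This matches the plan.

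**Effect of baseline remitters.** Let b be the share in remission at first administration, k the later remission rate in those patients, and r the rate in the others. The displayed rate is b·k + (1 − b)·r, so the excess over r is b·(k − r). It is zero if b = 0 or k = r, and negative if k < r (b = 0.10, k = 0.20, r = 0.30 gives 29%).

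The documents give neither b nor k. I assume b = 5% or 10% and k = 60% or 80%. For r I use the 30% of Protocol Table 1, and 14%, which is the 80:20 mix in Protocol Table 2 (0.8 × 10% + 0.2 × 30%). Both were set for full Mayo at Week 52; for partial Mayo they are illustrations.

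| b | k | r = 30% | r = 14% |
|---|---|---|---|
| 5% | 60% | 3.0 + 28.5 = 31.5% | 3.0 + 13.3 = 16.3% |
| 5% | 80% | 4.0 + 28.5 = 32.5% | 4.0 + 13.3 = 17.3% |
| 10% | 60% | 6.0 + 27.0 = 33.0% | 6.0 + 12.6 = 18.6% |
| 10% | 80% | 8.0 + 27.0 = 35.0% | 8.0 + 12.6 = 20.6% |

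The excess is 1.5 to 5 points for r = 30% and 2.3 to 6.6 points for r = 14%. Under NRI, missing status lowers k and r together; the same formula holds with the lower values.

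**In reverse.** If a table shows 30% of 315 (94.5 remitters), removing 16 patients (5%) leaves (94.5 − 9.6)/299 = 28.4% to (94.5 − 12.8)/299 = 27.3%. Removing 32 (10%) leaves (94.5 − 19.2)/283 = 26.6% to (94.5 − 25.6)/283 = 24.3%. The Wald half-width stays at 5.0 to 5.1 points.

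**McNemar test.** It uses only patients whose status changes. With 80 gains and 6 losses as an illustration, the exact p-value is 1.3 × 10⁻¹⁷ whether 0, 15 or 30 patients are in remission at both times. Patients who lose remission count against the drug.

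**Table 3.4.1.** I read the remission rule in SAP 10.3 as a partial Mayo score of 2 or below with no sub-score above 1. The strata in SAP 11 start at 0, 3 and 6, so every baseline remitter falls in the lowest one. Among scores of 0 to 2, the only combination that is not remission is one sub-score of 2 with the other two at 0. That part of the stratum therefore largely restates the outcome definition.

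**The case against.** Three tables already account for baseline. They are titled as changes in the remission rate, test each visit against first administration, and plot the rate by period; SAP 12.3 and 12.4 list first administration as a period. On a natural reading the baseline rate appears beside the later ones. This stands for the tests, and it is the reason not to replace the main rate there: limiting those tables to patients not in remission at the start would fix the baseline rate at 0%, rule out loss of remission and make the McNemar test degenerate. It does not separate the two groups in the later rates or their intervals.

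In Table 3.4.1 the two upper partial Mayo strata contain no baseline remitters, so their rates are clean. That stands for this one factor. The other factors are tested one at a time in all patients.

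A reader might infer that the SAP contradicts itself. It does not: Table 3.1.7.1 asks whether remission newly gained by Week 8 is kept at Week 52, and its exclusion belongs to that question. The difference in population needs an explanation, but it is not a conflict.

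A reader might also take the severity categories in Table 2.3 ("remission phase, mild, moderate and severe") and the stratum starting at 0 as proof that such patients were enrolled. Both may only reflect the full range of the scales. Eligibility should keep the share small, and the reference file on inclusion and exclusion of patients is not in the documents.

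**Conclusion.** The point holds in conditional form. The four tables state no exclusion for patients in remission at first administration, and nothing in SAP section 8 or 10.3 supplies one. The displayed rates and intervals are too high if such patients exist and are in remission later more often than the others. Under the assumed 5-10% and 60-80%, a 30% rate would show as 31.5-35%: from well under the planned half-width of 5.1 points to about equal to it.

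It is tempting to say that the remission rate is overstated. The documents do not show that, because they give neither the share in remission at the start nor its later rate. Nor does the point reach the McNemar tests, or the general improvement rate in Table 3.4, which is also called a primary endpoint but is not a remission measure. It is strongest for Table 3.4.1, which has no paired test and uses a factor that overlaps with its outcome.

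**What to change.** In Table 3.4.1, run the factor analysis in patients not in remission by partial Mayo score at first administration, and keep the all-patient result as a second line. The rule in Table 3.1.7.1 requires a baseline score, so also report how many patients have none. Expect the lowest partial Mayo stratum to become small.

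In Tables 3.1.2, 3.1.5.1 and 3.1.5.2, keep the all-patient rate and the McNemar test. State the number in remission at first administration. Add one line with the rate and Clopper-Pearson 95% CI among patients not in remission at that time, by full Mayo in 3.1.2 and by partial Mayo in the other two.

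The filter already exists in the SAP and no new data are needed. The cost is one extra line per table, a somewhat smaller denominator and a possibly less favourable rate. If no patient starts in remission, the count will show it and the question is closed.
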